3.1 General Design

The study is a double-blind, placebo-controlled trial investigating the pharmacologic response to celecoxib and naproxen in healthy adults. Subjects will be assigned to one of two treatment arms: a low dose arm and a high dose arm. Each treatment phase will be 7 days followed by a 3 day post-treatment assessment and a 2 week wash-out period. The order of the three treatment phases (celecoxib, naproxen, and placebo) will be randomized. The study schema is shown in the figure below:

Qualified subjects will have approximately 9 weeks of participation in this study (1 week/treatment phase x 3 treatment phases + 3 days/post-treatment assessment x 3 post-treatment assessments + 2 weeks/washout phase x 2 washout phases).

3.2 Primary Study Endpoints

The primary study endpoints are COX-1 and COX-2 activity as assessed *ex vivo* using whole blood assays and *in vivo* by measuring urinary excretion of prostaglandin metabolites.

3.3 Secondary Study Endpoints

Secondary outcome variables include:

- Celecoxib and naproxen pharmacokinetic profiles and drug exposure at steady state.
- 24 hr ambulatory blood pressure at steady state.
- Renal function as assessed by glomerular filtration rate (GFR), sodium & potassium excretion, aldosterone, and creatinine in 12-hour urine as well as renin, creatinine and urea nitrogen in plasma
- mRNA expression of genes in the COX pathway in lymphoblastoid cell lines derived from peripheral blood mononuclear cells (PBMCs).
- Analysis of the gut microbiome at steady state drug concentrations.
- Urinary and plasma metabolomics at trough and peak drug concentrations at steady state.
- Whole blood transcriptomics and plasma proteomics at trough and peak drug concentrations at steady state.
- DNA sequencing to identify genetic polymorphisms that modify the response to NSAIDs
- Nutritional assessment: 3-day food records, 24-hour dietary recalls and concentrations/ratios of major n-3/n-6 PUFAs in red blood cell membranes

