6.12.3 Visit 2 (Whole-Day Visit)

Subjects will arrive in a fasting state at the CTRC at approximately 7:30 AM on Treatment Day 7 and will be admitted as outpatients. All assessments are experimental and will be carried out for research purposes.

Blood pressure will be measured for 24 hours using an ambulatory blood pressure monitor. Activity will be measured using an actigraph digital activity recorder. A stool sample will be collected for assessment of the gut microbiome, and subjects will complete a questionnaire regarding food consumption over the previous 24 hours.

Blood will be drawn at approximately 7:50 AM for measurement of:

- COX-1 and COX-2 activity
- Transcriptomic analysis
- Proteomic analysis
- Metabolomic analysis
- NSAID plasma concentration
- Renin activity, creatinine, and urea nitrogen
- Concentrations/ratios of major n-3/n-6 PUFAs in red blood cell membranes

Spot urine will be collected for measurement of:

- Tx-M
- PGI-M
- PGE-M
- PGD-M
- Metabolomic analysis
- Urinary electrolytes, aldosterone, creatinine clearance, and glomerular filtration rate (GFR).

The study medication will be administered at 8 AM.

Blood will be drawn 0.5, 1, 2, 4, 8, and 12 hours after administration of the study medication for measurement of:

- COX-1 and COX-2 activity
- NSAID plasma concentration

Spot urine will be collected 1, 2, 4, 8, and 12 hours after administration of the study medication for measurement of:

- Tx-M
- PGI-M
- PGE-M
- PGD-M

At 4 hours after administration of the study medication (the presumed peak of drug concentrations), blood will also be drawn for measurement of:

- Transcriptomic analysis
- Proteomic analysis
- Metabolomic analysis

Urine will be collected over 12 hours for measurement of:

Urinary electrolytes, aldosterone, creatinine clearance, and GFR.

Subjects will be discharged after the 12 hour time point (approximately 8 PM).

CONFIDENTIAL

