Attachment 8: Study Advertisement Flyer
Attachment 9: Text of Electronic Advertisement

16.1 Study Procedures Flowchart

Event	Screening Visit		reatme Phase			-Treat				eatme hase			t-Treat				reatme Phase			-Treat	
Study Day		1	2-6	7	8	9	10		25	26- 30	31	32	33	34		49	50- 54	55	56	57	58 ⁴
Hours in CTRC	2	1	0	13	1	1	1		1	0	13	1	1	1		1	0	13	1	1	1
Informed Consent	Х																				
Medical History	х																				
Physical Examination	Х																				Х
Screening Labs	Х																				Х
Urine Drug Test	Х																				
Urine Pregnancy Test	Х	Х							Х							Х					Х
Serum Pregnancy Test	Х																				Х
Urinalysis	Х																				Х
Questionnaires (3-day food record and physical activity questionnaire)	х							weeks							weeks						
Study Drug Treatment		Х	Х	Х				t - 2	Х	х	Х				ıt – 2	Х	Х	Х			
DNA		Х						Nashout -	Х						Washout	Х					
PBMCs		Х						Was	Х						Was	Х					
Questionnaire (24-hour food recall)				Х							Х							Х			
Stool Sample				Х							Х							Х			
Plasma Drug Levels		Х		X ¹	Х	Х	Х		Х		X ¹	Х	Х	Х		Х		X ¹	Х	Х	Х
COX-1 acetylation		Х							Х							Х					
COX-1 and COX-2 Activity		Х		X ¹	Х	Х	Х		Х		X ¹	Х	Х	х		Х		X ¹	Х	Х	Х
Urinary Prostaglandins and Other Metabolites		х		X ¹	х	х	х		х		X ¹	х	х	Х		х		X ¹	х	х	х
Transcriptomics				X ²							X ²							X ²			
Proteomics				X ²							X ²							X ²			
Metabolomics				X ²							X ²							X ²			
24 hr Blood Pressure Monitoring				X ³							X ³							X ³			

Blood for plasma drug levels and COX-1 and COX-2 activity will be drawn before and 0.5, 1, 2, 4, 8, and 12 hours after taking the morning dose of study drug. Spot urine will be collected before and 1, 2, 4, 8, and 12 hours after taking the morning dose of study drug. 12 hr urine will be collected for assessment of creatinine clearance.

² Blood for transcriptomics, proteomics, and metabolomics will be drawn before and 4 hours after taking the morning dose of study medication.

³ Subjects will wear an ambulatory blood pressure and activity monitor for 24 hrs. The monitor will be removed when they return to the CTRC for the first Post-Treatment Assessment.

⁴ The Close-Out Visit will occur concurrently with the final visit of Post-Treatment Assessment 3.

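### Peak urinary metabolomics is a stated secondary endpoint, but the Day 7 schedule never assigns the 4-hour spot urine to that assay

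*Combined protocol and SAP*

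**What the plan says.** Section 3.3 gives the endpoint as "Urinary and plasma metabolomics at trough and peak drug concentrations at steady state".

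The Day 7 visit (section 6.12.3) sets out the sampling:

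- Before the morning dose, blood is drawn and spot urine is taken. Metabolomic analysis appears in both lists.
- After the dose, "Spot urine will be collected 1, 2, 4, 8, and 12 hours after administration of the study medication for measurement of" four analytes only: Tx-M, PGI-M, PGE-M and PGD-M.
- At the presumed peak, "At 4 hours after administration of the study medication (the presumed peak of drug concentrations), blood will also be drawn for measurement of" transcriptomic, proteomic and metabolomic analysis.
- A separate 12-hour urine collection serves electrolytes, aldosterone, creatinine clearance and GFR.

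In the flowchart (16.1), footnote 2 is attached to the transcriptomics, proteomics and metabolomics rows and reads "Blood for transcriptomics, proteomics, and metabolomics will be drawn before and 4 hours after taking the morning dose of study medication". Footnote 1 confirms the urine times: "Spot urine will be collected before and 1, 2, 4, 8, and 12 hours after taking the morning dose of study drug". A different row is labelled "Urinary Prostaglandins and Other Metabolites" and carries footnote 1 on Day 7.

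Section 6.8 describes metabolomics on plasma and urine but gives no sampling times.

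**The concern.** The endpoint asks for urine at peak, and the visit text does not send any peak urine for metabolomics. Staff who follow 6.12.3 to the letter would have no instruction to do so. Metabolomic analysis is listed for the spot urine on Day 1 (6.12.2), for the pre-dose spot urine on Day 7 and for the spot urine at each of the three post-treatment visits (6.12.4 to 6.12.6). It is absent only from the post-dose Day 7 urines, so the omission could easily be taken as intended.

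Section 6.8 also requires metabolomics samples to be moved to separately coded tubes and analysed by an outside collaborator. A tube labelled only for prostaglandin assays would not enter that route without an instruction.

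At stake is the trough-to-peak change in the urinary metabolome. The final report would have to explain why one component of a listed secondary endpoint was not measured.

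**Working it through.** There is no stated figure to reproduce. The check sets the endpoint's matrices and times against the Day 7 sample lists in 6.12.3.

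| Cell of the 3.3 endpoint | Specimen on Day 7 | Metabolomics listed for it? |
|---|---|---|
| Plasma, trough | Pre-dose blood | Yes |
| Urine, trough | Pre-dose spot urine | Yes |
| Plasma, peak | 4-hour blood | Yes |
| Urine, peak | 4-hour spot urine | No |

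Three of four cells are covered. The gap is 1/4 of the endpoint's cells, or 1/2 of its urine cells.

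Could another provision fill the fourth cell?

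1. *The 12-hour urine.* Metabolomics is not on its list, and a pooled 12-hour collection would not isolate the peak.
2. *Flowchart footnote 2.* It names blood only. It is weak evidence about urine, however. Its metabolomics row is marked only on the seventh day of each phase, so it also omits the urine metabolomics that the visit text lists on Day 1, at the Day 7 trough and after treatment.
3. *The flowchart row* "Urinary Prostaglandins and Other Metabolites". It is marked on Days 1, 7, 8, 9 and 10 of the first phase and the matching days of the others. Those are the days on which the visit text lists urine metabolomics. But on the same days the spot urine is also assigned to electrolytes, aldosterone, creatinine clearance and GFR, which have no row of their own. Section 6.3 also distinguishes the thromboxane metabolite from the prostaglandin metabolite. Any of these could be the other metabolites meant, so the pattern of days does not identify metabolomics.

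Assays needed to fill the cell:

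- Per subject: 1 four-hour urine x 3 phases = 3.
- All subjects: 3 x 288 = 864, if all 288 complete all phases.
- Of these, 2 x 288 = 576 come from active-drug phases and 288 from placebo phases. The placebo samples have no drug peak and serve as time-matched comparators.

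**The case against.** The strongest defence is that nothing is missing except a label. Both 6.12.3 and footnote 1 schedule a 4-hour spot urine in every phase. The flowchart row discussed above may have been meant to include metabolomics on those urines. Section 6.8 calls the metabolomics measurements exploratory, and section 7.2 treats the metabolomics analyses in the same way. No hypothesis, power calculation or decision depends on this cell.

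Most of this stands. It fixes the size of the point: an inconsistency in assay assignment within exploratory work. It does not remove the inconsistency, because the flowchart term is undefined and the visit text, which is the more detailed source, lists no metabolomics for that urine.

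A reader might infer two stronger things. One is that peak urine data are certain to be lost for every subject and drug. The documents do not support this: the specimen is taken, the flowchart leaves room for a wider reading, and the objectives in section 2 foresee biobanked samples, although no section specifies storage of the 4-hour urine. The other is that half of the endpoint goes unmeasured. The table shows one cell in four.

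**Conclusion.** Sections 3.3 and 6.12.3 do not agree. As the visit text stands, peak urine is the one cell of four without an assigned metabolomics assay, in each of the three phases. The specimen exists, so the defect lies in the assignment and not in the collection. The impact is minor: the primary endpoints, the sample size and the other three cells are unaffected.

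The conclusion takes 4 hours as the peak, as 6.12.3 does, and takes the visit text as what staff will follow. The subject handout summarising the visits (Attachment 3) was not available for this check, so it cannot be said whether it bears on the point.

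**What to change.** Choose one of two:

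- **Keep the endpoint.** In 6.12.3, add metabolomic analysis for the 4-hour spot urine that is already collected. In flowchart 16.1, give the metabolomics row a separate urine statement, and define what the other metabolites in the urinary row are. Leave footnote 2 as blood only. It also governs transcriptomics and proteomics, which 3.3 confines to whole blood and plasma, so widening it to urine would create a new contradiction. The cost is one aliquot per phase and up to 864 added urine assays, with no new collection.
- **Cut the endpoint.** In 3.3, restrict urinary metabolomics to trough and keep plasma at trough and peak. The cost is wording only, and the trough-to-peak comparison in urine is given up openly.

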3.4 Primary Safety Endpoints

Safety endpoints include:

- Renal function as assessed by glomerular filtration rate (GFR), sodium & potassium excretion, and creatinine in 12-hour urine as well as creatinine and urea nitrogen in plasma
- 24 hr ambulatory blood pressure at steady state

4 Subject Selection and Withdrawal

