1.4 Dose Rationale and Risk/Benefits

Celecoxib will be administered at a dose of 100 mg (low dose arm) or 200 mg (high dose arm) orally twice daily for 7 days. Naproxen will be administered at a dose of 250 mg (low dose arm) or 500 mg (high dose

arm) orally twice daily for 7 days. These dose regimens are clinically used in the treatment of rheumatoid arthritis, and are being used in the Prospective Randomized Evaluation Of Celecoxib Integrated Safety Vs Ibuprofen Or Naproxen (PRECISION) trial, ¹⁶ which is a prospective trial comparing the cardiovascular safety of celecoxib, naproxen, and ibuprofen. The half-lives of celecoxib and naproxen are 11 hours and 12-15 hours, respectively. Thus, the treatment duration of 7 days was chosen to ensure that drug plasma concentrations have reached steady state.

NSAIDs are generally considered safe drugs for short term treatments, and some NSAIDs are available as over-the-counter (OTC) painkillers in low doses. For example, naproxen is available OTC as a 200 mg dose. Higher does, including the doses used here (250 mg and 500 mg) require a prescription. Celecoxib is a prescription medicine at all doses. All NSAIDs may cause allergic reactions including asthma, urticaria, or allergic-type skin reactions and severe anaphylactic reactions. All NSAIDs can lead to the onset of new hypertension or worsening of preexisting hypertension. All NSAIDs may cause renal adverse events, including fluid retention and edema, and renal toxicity. All NSAIDs may cause gastrointestinal adverse events including heartburn, diarrhea, abdominal distress, nausea and vomiting, indigestion, constipation, abdominal cramps or pain, fullness of GI tract (bloating and flatulence), ulceration and bleeding. Chronic use of NSAIDs may increase the risk of myocardial infarction, stroke and thrombosis, although this has only been shown for celecoxib in randomized trials. Central nervous system adverse effects include dizziness, headache, nervousness, and tinnitus.

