5.2 Treatment Regimen

During each treatment phase, subjects will receive celecoxib, naproxen, or placebo for 7 days. Subjects will be assigned to either a high dose arm (celecoxib 200 mg BID, naproxen 500 mg BID, or placebo) or a low dose arm (celecoxib 100 mg BID, naproxen 250 mg BID, or placebo). Subjects will be instructed to take the study medications twice a day (at approximately 8 AM and 8 PM) on an empty stomach with a full glass of water.

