5.7 Packaging

Study drug will be supplied in bulk shipments and blinded by over-encapsulation by the IDS. The IDS will package blinded study medication on-site, as blister packs containing twelve capsules per blister pack. Each blister pack represents the drug supply for at-home drug treatment for a single treatment phase. The last dose, which will be administered on Day 7 in the CTRC, will be packaged separately. Subject

study drug supply will be packaged in kits of 3 blister packs plus the last study medication dose, one for each treatment phase. Each kit will represent the entire drug supply for one study subject.

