6.12.4 Visit 3 (Post-Treatment Visit 1)

Subjects will return to the CTRC at approximately 7:30 AM on the day after completing the treatment phase (Post-Treatment Assessment Day 1). At approximately 8 AM a spot urine sample will be collected for measurement of:

- Tx-M
- PGI-M
- PGE-M
- PGD-M
- Metabolomic analysis
- Urinary electrolytes, aldosterone, creatinine clearance, and glomerular filtration rate (GFR).

Blood samples will be drawn for measurement of:

- COX-1 and COX-2 activity
- NSAID plasma concentration

The ambulatory blood pressure monitor and actigraph will be removed, and subjects will be discharged.

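### The 24-hour blood pressure endpoint is labelled steady state, but about half the recording, including the whole night, falls after the last dosing interval

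*Combined protocol and SAP*

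**What the plan says.** Blood pressure is a secondary endpoint (Section 3.3) and one of two listed safety endpoints (Section 3.4), worded in both as "24 hr ambulatory blood pressure at steady state".

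The schedule around it is as follows:

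- Section 5.2: "Subjects will be instructed to take the study medications twice a day (at approximately 8 AM and 8 PM".
- Section 5.7: each phase has a blister pack of twelve capsules plus one more. "The last dose, which will be administered on Day 7 in the CTRC, will be packaged separately".
- Section 6.12.3 lists a single Day 7 dose, at 8 AM. It also states "Blood pressure will be measured for 24 hours using an ambulatory blood pressure monitor" and "Subjects will be discharged after the 12 hour time point (approximately 8 PM".
- Section 6.12.4, for a visit at about 7:30 AM on the day after treatment ends: "The ambulatory blood pressure monitor and actigraph will be removed, and subjects will be discharged".
- Section 16.1, footnote 3: "Subjects will wear an ambulatory blood pressure and activity monitor for 24 hrs".
- Section 1.4: "The half-lives of celecoxib and naproxen are 11 hours and 12-15 hours, respectively". The same paragraph chooses 7 days of treatment so that plasma concentrations reach steady state.

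Section 6.9 presets readings every 15 minutes from 0600h to 2200h, with a 20-minute option, and every 30 minutes from 2200h to 0600h. It takes awake and asleep times from diaries. It twice gives the recording length as 48 hours. Section 7 names no blood pressure window, summary or contrast.

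**The concern.** The endpoint label promises 24 hours under continued twice-daily dosing. The schedule records one dosing interval and then 12 hours of declining concentrations. A reader of the reported result would take it as the effect of regular use, night included, and the trial does not observe that.

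Section 1.4 lists new or worsened hypertension as a harm of all NSAIDs, and Section 4.1 admits people with controlled hypertension. If one 24-hour summary is reported under the steady-state label, it mixes two exposure levels and could make the rise during regular dosing look smaller than it is. The consequence is for the reported group result. The folder review of individual subjects in Section 16.5 does not depend on this summary.

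**Working it through.** **1. Dose count (the plan's own figure).** Days 1-6 twice daily give 6 x 2 = 12 doses, and Day 7 at 8 AM makes 13. The supply in Section 5.7 is 12 + 1 = 13, so it reproduces. An 8 PM dose on Day 7 would need a fourteenth capsule.

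**2. Timeline, in hours after the Day 7 dose.**

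| Period | Hours after last dose | Status |
|---|---|---|
| 8 AM-8 PM, Day 7 | 0-12 | regular dosing interval |
| 8 PM-10 PM | 12-14 | past the interval |
| 2200h-0600h | 14-22 | past the interval |
| 0600h-8 AM, Day 8 | 22-24 | past the interval |

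**3. Scheduled readings (Section 6.9).**

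- 15-minute setting: 0-12 h has 12 x 4 = 48; 12-24 h has 8 + 16 + 8 = 32; total 80.
- 20-minute setting: 0-12 h has 12 x 3 = 36; 12-24 h has 6 + 16 + 6 = 28; total 64.

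At the 15-minute setting, 48 of 64 clock-daytime readings and 0 of 16 night readings fall in the dosing interval. An awake/asleep split therefore does not separate the two exposure periods.

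**4. Exposure in 12-24 h relative to 0-12 h.** One-compartment model, 13 doses 12 h apart, k = ln 2 / half-life. By the last dose, mean 0-12 h concentration exceeds 99.9% of steady state.

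- Instant absorption: r = 0.5^(12/half-life), which is 0.469 (11 h), 0.500 (12 h) and 0.574 (15 h).
- First-order absorption: r = [ka·e^(-12k) - k·e^(-12ka)] / (ka - k). With ka from 2.0 down to 0.5 per hour (assumed), r is 0.485-0.537 (11 h), 0.515-0.565 (12 h) and 0.588-0.633 (15 h).

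The overall range is 0.469-0.633. For 2200h-0600h against 0-12 h the same model gives 0.463-0.628.

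**5. Shortfall of one 24-hour summary against 0-12 h, if effect is proportional to concentration (assumption).**

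- Time-weighted mean: 1 - (1 + r)/2. This is 1 - 1.469/2 = 0.265 down to 1 - 1.633/2 = 0.184, or **18-27%**.
- Plain mean of readings, 15-minute setting: (32/80) x (1 - r) = 0.4 x 0.531 = 0.212 down to 0.4 x 0.367 = 0.147, or **15-21%**.
- Plain mean, 20-minute setting: (28/64) x (1 - r) = 0.4375 x 0.531 = 0.232 down to 0.4375 x 0.367 = 0.161, or **16-23%**.
- Daytime mean, 0600h-2200h (hours 0-14 and 22-24): 0.090-0.130, or **9-13%**.

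The two plain-mean lines treat exposure as even within 12-24 h. Weighting by the actual reading density gives the same rounded ranges.

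**6. Other concentration-effect shapes (assumed).** With effect C/(C + EC50), time-weighted:

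| Mean 0-12 h concentration | Shortfall |
|---|---|
| 1 x EC50 | 0.114-0.180 |
| 3 x EC50 | 0.065-0.111 |
| 10 x EC50 | 0.026-0.048 |

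That is about 3-18% overall. If the effect persists unchanged through 24 h, the shortfall is 0%.

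**The case against.** The timeline and arithmetic are not in dispute. The case on the other side concerns how much they matter.

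- *No single 24-hour summary is actually planned.* Section 7 is silent on blood pressure, and the diaries in Section 6.9 suggest an awake/asleep split, whose daytime part would lose only 9-13% even under full proportionality. This stands in part: biased reporting is an inference. But the label is the only definition given, and an awake/asleep split still mixes exposure periods by day and has no dosing-interval readings by night.
- *Steady state may simply name the Day 7 visit.* Section 3.3 attaches the phrase to several Day 7 measures. Section 1.4, however, uses it for plasma concentrations, and hours 12-24 do not meet that sense.
- *The percentages rest on assumption.* This stands. The documents give no concentration-pressure relation, no expected effect in mmHg and no SD. Section 1.1 gives sodium retention as the mechanism, which may outlast 12 hours. What is established is that night-time concentration is below steady state, not that pressure is.
- *The placebo phase has the same schedule.* This also stands: a within-subject 24-hour difference is valid for the window recorded. Only its description is wrong.
- *Recording from 8 AM on Day 6 to 8 AM on Day 7 would deliver the endpoint as written.* It would, but Section 16.1 schedules no clinic time on Days 2-6, so it needs an extra visit in each of three phases.

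**Conclusion.** The concern holds. As scheduled, about 12 of 24 hours and all 8 preset night hours lie past the last dosing interval, so the endpoint in Sections 3.3 and 3.4 is not what will be measured. This follows from the dose count and visit times alone.

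The effect on a pooled 24-hour result ranges from 0% to 27% of the steady-state effect, depending on how pressure follows concentration, which the documents do not say. The upper end assumes proportionality and one-compartment kinetics with the protocol's half-lives. The point merits correction because this is a listed safety endpoint and the remedy is cheap. It does not touch the COX-activity primary endpoints.

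**What to change.** In Sections 3.3, 3.4 and 7.2:

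- Define the result as within-subject NSAID-minus-placebo differences in mean systolic and diastolic pressure at matching clock times, by dose arm, with 95% confidence intervals.
- Report these separately for 0-12 h after the Day 7 8 AM dose (the only steady-state window) and for 12-24 h (post-dosing). The split would also show whether the effect persists.
- Keep the 24-hour mean as supportive, without the steady-state label, and state that night-time pressure under continued dosing is not measured.

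In Section 6.9, change both mentions of 48 hours to 24. The 20-minute option is justified there by the 48-hour length, so fix one daytime setting or give another reason for the option.

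The cost is endpoint wording and a few tables, with no new visit, dose or assay. The 0-12 h window is daytime only, lies within a 13-hour clinic stay with six post-dose blood draws, and uses 48 of 80 readings (36 of 64 at the 20-minute setting). It is therefore less precise and less typical of daily life than a full 24-hour mean. The placebo phase shares the clinic setting, so that part is common to both sides of each difference.

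An added 8 PM dose on Day 7 is not preferred: it would move the Day 8-10 samples from about 24, 48 and 72 hours after the last dose to 12, 36 and 60. If steady-state night-time pressure is itself wanted, the Day 6 start is the option to cost.
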